#### D. Research Flow

#### E. Ethics

This research has been approved by Ethics Committee of the Faculty of Medicine Universitas Indonesia (Approval number: 981/UN2.F1/ETIK/2017)

#### IV. Statistical Analysis Plan

All Data will be analyzed using SPSS 24.0 (SPSS) for Windows. Laboratory parameters will be compared between two different times and also compared between two groups by using paired and independent t test (if normally distributed) or using Wilcoxon and Mann Whitney (if not normally distributed). Statistically significance was determined by p value <0.05. Intention to Treat analysis will be used. HIV symptom index and food frequency will be reported descriptively.

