### **B. Specific Objectives**

#### **a. Primary Objectives**

- i. To determine the average CD4 value in immunological non responder HIV patients treated with Probiotic compared to placebo
- ii. To determine the average T helper 17 value in immunological non responder HIV patients treated with Probiotic compared to placebo
- iii. To determine the average 16S rDNA value in immunological non responder HIV patients treated with Probiotic compared to placebo
- iv. To determine the fecal calprotectin value in immunological non responder HIV patients treated with Probiotic compared to placebo

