### C. Study Population

1. Targeted Population: HIV patients with Immunological Non-responder condition in Indonesia
2. Sample: HIV patients with Immunological Non-responder condition in Indonesia
3. Inclusion Criteria:
  - a. HIV positive patients aged 18-55 years old
  - b. had already treated with first line Highly Active Anti Retroviral Therapy for at least 6 months
  - c. had CD4 level of 200-410 cell/ $\mu$ L
  - d. undetectable Viral Load (<34 copies/ml blood)
  - e. agreed to participate in the study and signed the informed consent
4. Exclusion Criteria:
  - a. Pregnant patients
  - b. Lactating patients
  - c. Known *Lactobacillus* allergy
  - d. Body Mass Index (BMI) <16 kg/m^2
  - e. Under Tuberculosis treatment or other acute illness, acute diarrhea,
  - f. routinely taking selenium containing vitamin in last 1 month,
  - g. routinely consuming probiotics containing product in last 1 month
5. Estimation Sample Size: 80 samples. Which will be divided into two groups equally.
6. Study Procedure

[figure not shown]
Eligible patients will be approached to be enrolled in the clinical trial. Informed consent will be obtained. Patients will be randomized and divided into two groups, intervention and placebo group. Intervention group will receive Probiotics (Chewable tablet) containing *Lactobacillus plantarum*, *Streptococcus thermophiles*, *Bifidobacterium bifidum* once daily. While, Placebo group will receive placebo which had identical shape, flavor, and smell as the interventional drug.

Intervention will be held for 12 weeks. CD4, Th17, 16S Ribosomal RNA, and fecal calprotectin level will be checked at the 0 week and repeated after 12 weeks of intervention. Self administered HIV Symptoms Index questionnaire will be filled by the respondent on 0,4,8,12 weeks of intervention. Food frequency questionnaire will be filled by the respondents with the help of nutritionist on 0,4,8,12 weeks of intervention.

7. Side effects

All side effects that may arise and related to probiotics intake will be assessed and reported. Appropriate medical advice will be provided.

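### The plan tests week 0 against week 12 for significance beside the between-arm test and does not say which decides, although every primary objective is a comparison with placebo

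*Combined protocol and SAP*

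**What the plan says.** Section IV (Statistical Analysis Plan) sets out two comparisons for the laboratory markers in one sentence: "Laboratory parameters will be compared between two different times and also compared between two groups by using paired and independent t test". The non-parametric alternatives are paired up in the same way: "using Wilcoxon and Mann Whitney (if not normally distributed". One criterion then covers everything: "Statistically significance was determined by p value <0.05". The section does not name the between-group test as decisive and does not call the time comparison descriptive. It does use a descriptive label elsewhere, for the HIV symptom index and the food frequency data.

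The primary objectives (II.B.a) cover CD4, Th17, 16S rDNA and fecal calprotectin, and each is a comparison with placebo. For CD4 it reads: "To determine the average CD4 value in immunological non responder HIV patients treated with Probiotic compared to placebo".

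Section III.C gives the remaining facts:
- **Size:** "Estimation Sample Size: 80 samples", followed by "Which will be divided into two groups equally", which makes 40 per arm.
- **Timing:** each marker's "level will be checked at the 0 week and repeated after 12 weeks of intervention", so each patient has one before-after pair per marker.
- **Entry:** patients "had CD4 level of 200-410 cell"s/µL and at least 6 months of first-line antiretroviral therapy (ART).

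**The concern.** A paired test in one arm asks whether the mean changed over 12 weeks. That null hypothesis can be false in both arms when the probiotic does nothing. If CD4 rises for a reason common to both arms, the probiotic arm's paired test becomes more likely to be significant as the rise grows, while the difference between arms stays at zero.

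The entry criteria allow two such reasons. Patients may still be recovering CD4 on ART. They are also selected on a bounded CD4 window, so a repeat value may regress toward the population mean if the qualifying value is also the week-0 value.

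At stake is how the result is reported. With two unranked significance tests, a significant rise on probiotic beside a non-significant change on placebo could be presented as evidence of effect, even when the direct comparison of the arms shows nothing. The same logic applies to the other three markers. The figures below are for CD4 only.

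**Working it through.** **The plan's own figure.** The total of 80 cannot be reproduced, because no effect size, SD, power or dropout is given with it. Only 80 / 2 = 40 per arm is used here.

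**Inputs from the documents.** n = 40 per arm; threshold 0.05; one week-0 and one week-12 value per patient.

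**Assumptions, none of them in the documents.** Two-sided testing (sidedness is not stated); no probiotic effect; the same mean CD4 rise in both arms; normally distributed changes; SD of change 63.6 or 84.9 cells/µL (about 64 to 85).

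**Step 1: paired test in one arm.** The statistic follows a noncentral t distribution with 39 degrees of freedom and noncentrality = drift / (SD / √40). The standard error is 63.6 / √40 = 10.06 or 84.9 / √40 = 13.42. At a drift of 20 cells, for example, the noncentrality is 20 / 10.06 = 1.99 or 20 / 13.42 = 1.49.

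**Step 2: probiotic significantly up, placebo not significant.** The arms are independent, so the probability is u × (1 − p). Here u is the chance of a significant rise and p the chance of significance in either direction. With no drift this is 0.025 × 0.95 = 0.024.

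| Shared rise (cells) | SD 63.6: u × (1 − p) | SD 84.9: u × (1 − p) |
|---|---|---|
| 0 | 0.025 × 0.950 = 0.024 | 0.025 × 0.950 = 0.024 |
| 5 | 0.070 × 0.923 = 0.065 | 0.055 × 0.935 = 0.051 |
| 10 | 0.161 × 0.837 = 0.135 | 0.109 × 0.888 = 0.097 |
| 15 | 0.307 × 0.693 = 0.213 | 0.192 × 0.807 = 0.155 |
| 20 | 0.492 × 0.508 = 0.250 | 0.306 × 0.694 = 0.212 |
| 25 | 0.679 × 0.321 = 0.218 | 0.443 × 0.557 = 0.247 |

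At 15 to 25 cells the probiotic arm's paired test alone is therefore significant in 19% to 68% of trials. The split pattern cannot exceed about 25%, because p(1 − p) peaks at p = 0.5. At larger drifts it falls, because both arms become significant.

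**Step 3: the between-arm test.** A shared rise cancels in the difference between arms. In simulation (50,000 trials per scenario, t test on change scores, shared drift of 0 to 0.5 SD) it rejected in 4.9% to 5.0% of trials, so about 2.5% in the favourable direction. At drifts of 0.2, 0.3, 0.4 and 0.5 SD the same simulation gave the split pattern in about 18%, 25%, 21% and 11% of trials. A significant probiotic-arm rise with a non-significant between-arm test occurred in 21%, 43%, 67% and 84%.

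**Step 4: how large could shared drift be?** The documents do not say. Regression to the mean was simulated with lognormal true CD4 and proportional within-person error, selecting observed values of 200 to 410 and treating the selected value as week 0.
- Population mean 350 to 450, SD 130 to 200, within-person CV 15% to 20%: a rise of about 6 to 42 cells.
- Population mean 280 to 300, same SDs and CVs: about 1 to 5 cells.

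The size thus depends heavily on the assumed population. No figure for continued ART recovery can be derived from the documents.

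**The case against.** The strongest reply is that the misuse is inferred. The trial is randomized and double-blind, the objectives are comparisons with placebo, and the between-group test is in the plan. Read together, these already point to the test that answers the question, and a between-arm result would appear in the same report. Much of this stands. A reader might infer that the plan intends to claim efficacy from a paired p value, but the documents nowhere say so. They are only silent on which test decides.

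Three further points are fair:
- **A paired test is not invalid.** If CD4 truly rises in both arms, rejecting no change is correct. Only an inference from it to a treatment effect would be wrong. The percentages for the split pattern are the frequency of a result that invites misreading, not the error rate of a rule that the plan adopts.
- **Testing within each arm is a reading.** The text speaks of two times. A test pooled over both arms is possible on the wording, but it would say even less about treatment.
- **Drift is not established.** With none, the split pattern is no more frequent than a favourable false positive from the between-arm test. Regression to the mean matters only if the qualifying CD4 is also the week-0 value, which the text does not settle. A separate baseline draw would remove most of it.

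It can also be said that one sentence ranking the tests would suffice and the paired p values could stay. That sentence is the essential part. But the paired tests serve no stated objective, and the change in each arm can be shown without them.

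**Conclusion.** The point holds as a fault of specification that should be corrected. The plan places a significance test that answers none of its primary objectives beside the one that does, under the same threshold and without a ranking. With no probiotic effect, 40 per arm and an SD of change of 64 to 85 cells/µL, a significant rise on probiotic without significance on placebo occurs in about 2.4% of trials at zero shared drift, 5-7% at 5 cells, 10-14% at 10 cells and 16-25% at 15 to 25 cells. The between-arm test gives 2.5% in the favourable direction throughout. The SDs and drifts are assumptions, so the upper figures apply only if a shared rise of that size occurs.

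The documents do not support the stronger conclusions that CD4 will drift, that the between-arm test is compromised, or that the plan commits to an invalid efficacy claim.

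**What to change.** In Section IV:
1. State that conclusions about a probiotic effect rest only on the between-arm comparison, and that a change within one arm, or a contrast between one arm's significance and the other's, will not be presented as evidence of effect.
2. Remove the paired t and Wilcoxon tests as significance tests. Report the week-0 to week-12 change in each arm descriptively, as mean with SD or confidence interval, or median with interquartile range. If a confidence interval is shown, its exclusion of zero should not be read as a treatment result.

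The between-arm false-positive rate per marker then stays at 5% whatever the shared drift. The change is to wording only, with no added patients, visits or assays. What is lost is the within-arm p values.

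### Between-arm laboratory tests ignore the week-0 values already collected; ANCOVA on a scale fixed in advance would usually gain precision with no new data

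*Combined protocol and SAP*

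**What the plan says.** Section IV (Statistical Analysis Plan) states that "Laboratory parameters will be compared between two different times and also compared between two groups", using "paired and independent t test (if normally distributed) or using Wilcoxon and Mann Whitney (if not normally distributed". It names no covariate, adjusted model, transformation or effect measure, and it does not say whether the arms are compared on week-12 values or on change from week 0. The threshold is given as "Statistically significance was determined by p value <0.05".

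Section III.C, under Study Procedure, provides the baseline data: "CD4, Th17, 16S Ribosomal RNA, and fecal calprotectin level will be checked at the 0 week and repeated after 12 weeks of intervention". These are the four primary markers of section II.B, reading the 16S ribosomal RNA of the procedure as the 16S rDNA of the objectives. The first objective is worded "To determine the average CD4 value in immunological non responder HIV patients treated with Probiotic compared to placebo", with no time point. The sample size is "80 samples. Which will be divided into two groups equally", so 40 per arm. Patients enter only if they "had CD4 level of 200-410" cells/µL.

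**The concern.** Each primary marker has its own baseline value, and the between-arm test makes no stated use of it as a covariate. The paired or Wilcoxon comparison of the two times does not fill the gap, because a within-arm change does not estimate probiotic against placebo.

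This is a matter of efficiency and pre-specification, not bias. A test of week-12 values and a test of changes are each valid under randomisation if one is fixed in advance. The wording leans towards week-12 levels, since the objectives speak of an average value and week 12 is the only on-treatment laboratory time point, but it does not settle the matter. On either reading, with so few patients, part of the available precision may be given up for nothing.

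A lesser point is that choosing the test by observed distribution lets the sample decide whether a mean difference or a rank comparison is reported for each primary marker.

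**Working it through.** **Inputs.** From the documents: 40 per arm, significance level 0.05, one week-0 and one week-12 value per marker. Assumed, because the documents are silent: two-sided testing, a true effect of 0.5 SD, equal SDs at the two times, and a week-0/week-12 correlation r of 0.3, 0.5 or 0.7. The plan states no power, so there is no figure of its own to reproduce.

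**1. Near-normal marker.** Variance relative to an unadjusted week-12 comparison:

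- week-12 values: 1
- change from week 0: 2(1 − r)
- ANCOVA: (1 − r²)(1 + 1/76), where 1/76 (about 1.3%) is the cost of estimating the slope with 80 patients

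Power comes from the noncentral t distribution with noncentrality 0.5/√(2v/40), where v is the relative variance; degrees of freedom are 78, or 77 for ANCOVA. For week-12 values this is 0.5/0.2236 = 2.24. For ANCOVA at r = 0.5, v = 0.75 × 1.0132 = 0.760 and the noncentrality is 0.5/0.1949 = 2.57.

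| | r = 0.3 | r = 0.5 | r = 0.7 |
|---|---|---|---|
| Week-12 t test, power | 60% | 60% | 60% |
| Change t test, power | 46% | 60% | 81% |
| ANCOVA, power | 63% | 72% | 87% |
| 95% CI half-width, week-12 (SD) | 0.445 | 0.445 | 0.445 |
| 95% CI half-width, ANCOVA (SD) | 0.43 | 0.39 | 0.32 |
| Patients per arm for an unadjusted week-12 test to match ANCOVA, 40/v | 43 | 53 | 77 |

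Simulation of 40,000 trials per correlation gave ANCOVA power of 63.3%, 72.2% and 86.6%. At r = 0, ANCOVA loses about 0.6 points (59.2% against 59.8%). It breaks even with the week-12 test where (1 − r²)(77/76) = 1, that is r = √(1/77) = 0.114.

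**2. CD4 and the entry window.** Assume CD4 is normal with mean 300-350, SD 120-200 and correlation c = 0.6-0.8 before selection, then restrict entry to 200-410.

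*If the entry value is also the week-0 value.* Let k be the ratio of the truncated to the untruncated variance. Then r = c√[k/(c²k + 1 − c²)]. For mean 325, SD 160 and c = 0.7, k is about 0.135 and r about 0.34. Power is 59.8% for week-12 values, 64.1% for change and 64.5% for ANCOVA, the last equivalent to about 45 per arm (40/0.897). Over the whole grid r is 0.22-0.54. With the slope cost counted, ANCOVA gains 1.5 to 14 points over week-12 values and −0.2 to 1.8 over change.

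*If entry CD4 is a separate earlier measurement* (correlation 0.6-0.9 with week 0), r is 0.26-0.61, and ANCOVA gains 2-19 points over week-12 values and 5-14 over change.

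**3. Skewed marker.** Lognormal simulation, 10,000 trials per correlation; paired figures are for r = 0.3/0.5/0.7.

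| | Mann-Whitney, week 12 | ANCOVA, raw scale | ANCOVA, log scale |
|---|---|---|---|
| Log-SD 1.0, ratio 0.6 | 59-60% | 46/52/63% | 66/74/88% |
| Log-SD 0.5, ratio 0.78 | 56-58% | 58/66/79% | 64/72/86% |

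Null rejection at log-SD 1.0 was 0.041-0.053 for all methods.

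**4. Choosing the test by distribution.** The plan names no normality check, so a Shapiro-Wilk test at 0.05 in each arm was assumed. At log-SD 1.0 the switching procedure on week-12 values had 59-60% power, against 62-63% for an unadjusted log-scale t test: a cost of 2-3 points.

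**The case against.** The plan contains no error here. Its tests are valid, so the case for changing them rests on the size of the gain, and that depends on a correlation the documents do not give. At r = 0.3 the gain is only about 3.5 points, and below about 0.11 there is a slight loss. CD4, the first-listed primary marker, is where the gain may be smallest: the central same-value case is worth 4 to 5 patients per arm, not the 13 that r = 0.5 implies, and against a change-score test the advantage can vanish. ANCOVA also brings choices of its own. A poor choice of scale can cost power, and undetectable values need a rule. With half the values undetectable and replaced by half the limit (log-SD 1), a simulation still showed log-scale ANCOVA ahead, but by about 3, 9 and 19 points at underlying correlations of 0.3, 0.5 and 0.7.

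All of this stands as a limit on size, and the 13-patient figure should be read as one point in a range. None of it removes the gain at moderate correlation or shows a material loss on a suitable scale. The entry window applies to CD4 only; the other three markers have none.

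Two further points are fair. With the week-0 value as covariate on the same scale, ANCOVA of the week-12 value and ANCOVA of the change give the same arm effect, so naming week 12 matters for the Mann-Whitney sensitivity analysis rather than for the main model. And different effect measures across markers are not a fault in themselves, since the proposal uses them too; the fault is leaving the choice to the sample.

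**Conclusion.** The concern holds. The between-arm comparison makes no adjustment for baseline values the trial already collects, and an adjusted analysis on a suitable scale is at least as precise as the week-12 or the change comparison, apart from about 1% of variance. For a near-normal marker with 40 per arm and a 0.5 SD effect, the gain over the week-12 test is about 3.5, 12 and 27 points of power at correlations of 0.3, 0.5 and 0.7; the worst case, at zero correlation, is a loss of about 0.6 points. For CD4 it may be as little as 1.5 points over week-12 values, and nil over change, if the entry measurement doubles as week 0.

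The direction is secure for any correlation above about 0.11 on a suitable scale. The size is only moderately certain, because the SD, correlation, effect size and marker distributions are all assumed. The planned analysis is not invalid; this is a change that should be made because it is cheap and the sample is small.

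**What to change.** In section IV:

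- State that the between-arm comparison is of week-12 values.
- For each of the four laboratory markers, pre-specify ANCOVA of the week-12 value on randomised arm, with that marker's week-0 value as covariate.
- Fix each marker's scale before unblinding: for example CD4 untransformed, and the log scale for markers expected to be right-skewed, reported as a ratio of geometric means. Add a stated rule for undetectable values.
- Report the adjusted difference or ratio with its 95% CI, and keep Mann-Whitney as a sensitivity analysis in place of the distribution-based switch.

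The cost is a few sentences of SAP text and one model per marker in the software already named. No extra data, visits or patients are needed. Patients without a week-12 value need a handling rule under either analysis.

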**Approved May 1st, 2018**

## **I. Background**

Human Immunodeficiency Virus (HIV) infected patients treated with anti retroviral drugs may experiencing immunological failure known as immunological non responders (INR). In this particular group of patient, the level of CD4 still below normal limit even though the HIV virus is suppressed (undetected). Immunological non responders (INR) were associated with high morbidity. Hypothetically, INR patients have decreased gut integrity and immunity due to increased gut inflammation and further causing microbial translocation. Probiotics may improved gut inflammation condition, however the direct benefits of probiotics supplementation for INR HIV patients have not been studied. Growing number of INR HIV patients will be associated with higher economical burden and decreased quality of life.

Microbial translocation was thought as the underlying mechanism of persistently immune activation which may lead to immunological failure condition in virally suppressed HIV patients. Decreased number of T- helper 17 (Th17) in HIV patients may facilitated microbial translocation. HIV Virus destroyed the CD4 T memory cells which mainly found in *gut associated lymphoid tissue* (GALT), thus resulting in lower production of Th17 in gut mucosal tissue. One of the microbial translocation marker is 16S ribosomal DNA (16S rDNA) bacteria blood level. Gut inflammation may be represented by fecal calprotectin level.

Probiotics supplementation in HIV patients was proposed may increase gut integrity and immunity through several mechanisms: improving tight junction gut mucosal, increasing mucin production, regulating Th17; therefore decreasing gut inflammation and microbial translocation. Improved gut inflammation and decreased microbial translocation may increased the immune recovery in INR HIV patients

This clinical trial is intended to evaluate the immune recovery effect of Probiotics supplementation in INR HIV patients.

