## **II. Objectives**

### **A. General Objectives**

To determine the effect of Probiotic in immune response for immunological non responder HIV patients

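### Four unranked primary endpoints are each tested at p<0.05 with no rule for success; if any one significant marker were to count, the false-positive chance would exceed 5%

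*Combined protocol and SAP*

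**What the plan says.** Section II.A gives one general objective: "To determine the effect of Probiotic in immune response for immunological non responder HIV patients". The Background states one purpose in similar terms: "This clinical trial is intended to evaluate the immune recovery effect of Probiotics supplementation in INR HIV patients".

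Section II.B.a lists four primary objectives, each framed against placebo:

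- CD4: "To determine the average CD4 value in immunological non responder HIV patients treated with Probiotic compared to placebo"
- Th17: "To determine the average T helper 17 value in immunological non responder HIV patients treated with Probiotic compared to placebo"
- 16S rDNA: "To determine the average 16S rDNA value in immunological non responder HIV patients treated with Probiotic compared to placebo"
- Fecal calprotectin: "To determine the fecal calprotectin value in immunological non responder HIV patients treated with Probiotic compared to placebo"

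They are numbered i to iv, but the numbering is not said to be a testing order, and none is marked as the main endpoint.

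Section IV describes the tests: "Laboratory parameters will be compared between two different times and also compared between two groups by using paired and independent t test", with rank-based alternatives if the data are not normal. It then gives a single threshold: "Statistically significance was determined by p value <0.05". The secondary outcome, the HIV symptom index, is reported descriptively, so the laboratory tests carry all of the formal inference.

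**The concern.** The protocol asks one overall question and provides four primary answers to it. It does not say which pattern of results would count as yes. One significant marker out of four could be reported as a met primary objective and as evidence of an effect on immune response. The same result could equally be called a failure on three of four. With nothing written down, the rule can be chosen once the results are known. If the rule chosen is the most generous one, the overall conclusion is no longer held at 5%.

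Two further gaps in Section IV bear on the same conclusion:

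- The between-arm contrast is not specified. It could be the week-12 value, the change from week 0, or a baseline-adjusted comparison.
- The within-arm before-and-after tests use the same threshold and are not set apart from the between-arm tests, although every primary objective is a comparison with placebo.

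**Working it through.** **What can be reproduced.** The 0.05 level is declared, so there is nothing to derive. No family-wise error rate is stated. The sample size of 80 cannot be reproduced, because no effect size, SD, power or dropout rate is given.

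**Inputs from the documents.**
- Four primary endpoints (II.B.a).
- Threshold 0.05 per test (IV).
- 80 patients in two equal groups, so 40 per arm (III.C, item 5).
- Laboratory measurements at weeks 0 and 12 only (III.C, item 6), so there is one follow-up time per endpoint.

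**Assumptions not in the documents.**
- Two-sided tests, each holding its nominal level.
- A common correlation r between the four test statistics.
- No product effect on any marker.
- One fixed between-arm contrast per endpoint.

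**Any-one reading, four between-arm tests.**
If independent: 1 − (1 − 0.05)^4 = 1 − 0.95^4 = 0.1855.
If equally correlated: 1 − P(all four |Z| < 1.96), by numerical integration over the shared normal factor.

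| Assumed r | Chance of at least one false positive |
|---|---|
| 0 | 18.5% |
| 0.3 | 17.4% |
| 0.5 | 15.6% |
| 0.7 | 13.0% |
| 0.9 | 9.4% |

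Under any dependence the chance is at most 4 × 0.05 = 20%. Simulated t tests with 40 per arm (100,000 trials) gave 18.6% at r = 0 and 15.7% at r = 0.5. If the tests were one-sided at 0.05, the figure at r = 0.5 would be 14.4%.

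**Other readings.**
- Each marker as its own question: each answer keeps its 5% error.
- All four required: the error is at most 5%, because the claim can be no more likely than significance on any single endpoint that has no effect.

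**With Holm across the four.** With no effect on any marker, a false claim requires the smallest p value to pass 0.05/4 = 0.0125. The chance is 1 − 0.9875^4 = 4.9% at r = 0, 4.7% at r = 0.3 and 4.3% at r = 0.5.

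**If the contrast stays open.** Suppose the better of week-12 value and change could be chosen for each endpoint after the data are seen. Simulation with 40 per arm and an assumed week-0 to week-12 correlation of 0.3 to 0.7 gives an any-one error of about 8% to 9% even with Holm. A single CD4 test gives about 9%. A multiplicity rule therefore does not hold the error at 5% unless the contrast is also fixed.

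**Power cost of Holm.** From the noncentral t distribution with 40 per arm, an effect giving 80% power at 0.05 gives 61.1% at 0.0125. In detectable difference at 80% power (normal approximation): (1.960 + 0.842) × √(2/40) = 0.63 SD at 0.05, and (2.498 + 0.842) × √(2/40) = 0.75 SD at 0.0125.

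**The case against.** The best counter-argument is that the inflation comes from a rule the plan does not contain. Section II.B.a poses four separate questions, one per marker. Answering distinct questions at 5% each, and reporting all of them, is a recognised position. The Background also treats gut inflammation and microbial translocation as steps leading to immune recovery, so a careful reader would not take an isolated calprotectin result as immune recovery. In addition, this is an 80-patient biomarker trial at one hospital, and all four named results would be visible.

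Much of this stands. A reader might infer from the two sections that the trial's false-positive rate is 16% to 19%. The documents do not support that: they state no any-one rule, no correlation and no sidedness. The figure belongs to one permitted reading, and it is lower at high correlations, which the shared mechanism in the Background makes possible.

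A reader might also add the within-arm tests to the family and arrive at a larger figure. Nothing says that those tests answer the primary objectives, which ask only between-arm questions, so they are left out of the arithmetic.

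What remains is that the protocol places all four markers under one general objective, labels all four primary, never calls the trial exploratory, and leaves the success rule unstated. The any-one reading is weakened but not excluded.

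**Conclusion.** The concern holds in conditional form. The defect is an unstated success rule for four unranked primary endpoints, each tested at an unadjusted 0.05. If any one significant marker were taken as an effect, the chance of a false positive would lie between 18.5% (independent tests) and 9.4% (correlation 0.9). These figures rest on the assumptions of two-sided tests, equal correlation, a fixed between-arm contrast and no product effect. Every value examined exceeds 5%, and the one-sided figure does too, so the direction does not depend on these assumptions although the size does. Under separate-question or all-four readings there is no inflation. It is not established that the plan as written has an inflated error rate, only that nothing in it prevents one. This should be fixed, but it does not invalidate the design.

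**What to change.** Before unblinding, amend II.B and IV to settle three things.

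(a) **One between-arm contrast per endpoint**, used for every primary test. An example is the week-12 value adjusted for the week-0 value, which is already collected.

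(b) **One success rule**, chosen from:
- *Holm.* Family-wise error is controlled at two-sided 0.05 by Holm across CD4, Th17, 16S rDNA and fecal calprotectin, and benefit is claimed only for endpoints significant after Holm. This suits a claim that may rest on any one marker.
- *Single primary.* CD4 is the only primary endpoint, tested at two-sided 0.05, and the other three are secondary. This suits a claim of immune recovery, since the Background describes non-response by CD4 and the inclusion criteria select on it. The documents do not compel this choice.

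(c) **Status of the within-arm paired comparisons:** descriptive, supporting no claim of product effect.

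The timing matters: choosing between the two rules after seeing results would recreate the problem.

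The cost is wording only, with no new data. Under Holm, an endpoint with 80% power at 0.05 has about 61% at the first step; the 80% is assumed, because the documents give no power. The single-primary option keeps the full 0.05 for CD4, and the other three markers lose primary status.
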